## **7.4 Dose Escalation**

Participants who do not experience an objective response within 2-4 cycles of starting treatment with ponatinib may be candidates for dose-escalation of ponatinib to a dose of 45 mg once daily, provided the following criteria are met: 1) the participant has not experienced any vascular toxicities of any grade, 2) the participant has not experienced any grade 3/4 treatment-related toxicities, and 3) the treating investigator receives approval from the study Sponsor.

In addition, participants who achieve an objective response to therapy but subsequently relapse may also be candidates for dose escalation to a ponatinib dose of 45 mg once daily, provided the same criteria above are met.

## **7.5 Management of Selected Adverse Events**

### **7.5.1 Vascular Occlusion**

Arterial and venous thrombosis and occlusions have occurred in at least 27% of ponatinib treated patients, including fatal myocardial infarction, stroke, stenosis of large arterial vessels of the brain, severe peripheral vascular disease, and the need for urgent revascularization procedures. Patients with and without cardiovascular risk factors, including patients less than 50 years old, experienced these events. Monitor for evidence of thromboembolism and vascular occlusion. Interrupt or stop ponatinib immediately for vascular occlusion. If a participant experiences an arterial thrombotic event while receiving ponatinib, the subject should discontinue ponatinib permanently. Please see [Section 6.11](#) for a list of required concomitant therapy in order to minimize the risk of arterial thrombotic events. In participants with venous thrombosis or occlusion, a benefit-risk consideration should guide a decision to restart ponatinib therapy. This should be done in collaboration with the study Principal Investigator.

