### **7.3 Dose Delay and/or Reduction for Adverse Events (AEs) Attributable to the Study Drug**

[Table 7.1](#) describes suggested guidelines for dose modification due to study-drug-related toxicity, graded according to NCI CTCAE 4.0. However, for an individual participant, dose interruptions, reductions and treatment discontinuation should also be based on the clinical circumstance and investigators should use clinical judgment in deciding whether a dose reduction, delay or discontinuation is appropriate for any given clinical circumstance. In general, when the observed toxicity has resolved to  $\leq$  grade 1, the investigator may resume full dosing if clinically indicated.

No dose reduction below 15 mg once daily is permitted for ponatinib. If the participant cannot tolerate a minimum dose of 15 mg per day of ponatinib, despite any allowed interruptions, the participant must be discontinued from study treatment. Doses may be interrupted for study-drug related toxicities for up to 28 days. If a non-hematologic study-drug related toxicity does not resolve to Grade 1 or less after dose interruption for more than 28 days, the participant must be discontinued from study treatment. If a hematologic study-drug related toxicity does not resolve to Grade 1 or less after dose interruption for more than 28 days, the Principal Investigator/Sponsor must be contacted. Additionally, the Principal Investigator/Sponsor must be contacted if any adverse event deemed unrelated to treatment requires dose interruption for more than 28 days. Lastly, for each participant, once a dose reduction has occurred, the dose level may not be re-escalated during subsequent treatment cycles of ponatinib.

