**Table 7.1 Ponatinib: Dose Modifications for Drug Adverse Reactions**

Toxicity	Modification
Nonhematologic Toxicity	
General (Any CTCAE v4.0 nonhematologic toxicity not otherwise specified below)	
Grade 1 or transient Grade 2	No intervention
AST/ALT Elevations	
Grade 1 or transient Grade 2	No intervention
Grade 2 lasting $\geq$ 7 days with optimal care AND total bilirubin $<$ 2 x ULN	Hold ponatinib Resume at 30 mg after recovery to $\leq$ grade 1  Recurrence at 30 mg: Hold ponatinib Resume at 15 mg after recovery to $\leq$ grade 1  Recurrence at 15 mg Discontinue ponatinib
Grade 3 or 4 AND total bilirubin $<$ 2 x ULN	Hold ponatinib Resume at 30 mg after recovery to $\leq$ grade 1  Recurrence at 30 mg Hold ponatinib Resume at 15 mg after recovery to $\leq$ grade 1  Recurrence at 15 mg Discontinue ponatinib
Grade $\geq$ 2 AND total bilirubin $\geq$ 2 x ULN (In the absence of liver metastases)	Discontinue ponatinib
Pancreatitis	
Grade 2 (enzyme elevation or radiologic findings only)	See amylase/lipase section below
Grade 3 (severe pain, vomiting, medical intervention indicated [eg, analgesia, nutritional support])	Hold ponatinib Perform ultrasound or abdominal CT scan with contrast If imaging is positive, continue holding ponatinib and repeat according to clinical care. If imaging is negative, or after resolution by imaging, resume at 15 mg after recovery to $\leq$ grade 1  Recurrence at 15 mg: Repeat above Consider discontinuing ponatinib
Grade 4	Hold ponatinib Consult sponsor
Amylase/Lipase	
Grade $\leq$ 2	No intervention; monitor closely

Toxicity	Modification
Grade 3 with no radiologic findings	Hold ponatinib Resume at 30 mg after recovery to $\leq$ grade 1  Recurrence at 30 mg: Hold ponatinib Resume at 15 mg after recovery to $\leq$ grade 1  Recurrence at 15 mg: Discontinue ponatinib
Grade 3 with radiologic findings or Grade 4	Hold ponatinib Repeat imaging according to clinical care After resolution by imaging, resume at 15 mg after recovery to $\leq$ grade 1  Recurrence at 15 mg: Discontinue ponatinib
LV dysfunction/CHF	
Grade 2 or 3	Hold ponatinib Resume at 30 mg after recovery to $\leq$ grade 1  Recurrence at 30 mg: Hold ponatinib Resume at 15 mg after recovery to $\leq$ grade 1  Recurrence at 15 mg: Discontinue ponatinib
Grade 4	Discontinue ponatinib
Skin rash	

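### For low-grade vascular occlusion, Table 7.1's General row and Section 7.5.1 give opposite instructions, and the protocol does not say which governs

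*Combined protocol and SAP*

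**What the plan says.** Four places in Section 7 bear on what a site does when a participant has a vascular event.

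- **Section 7, opening paragraph.** Sites are referred to Table 7.1 and to Section 7.5 together. No order of precedence is given.
- **Table 7.1.** The named rows cover AST/ALT, pancreatitis, amylase/lipase, LV dysfunction/CHF, skin rash and ANC/platelets. None is vascular. The General row covers "Any CTCAE v4.0 nonhematologic toxicity not otherwise specified below", and its one visible line prescribes no intervention for grade 1 or transient grade 2.
- **Section 7.3.** Table 7.1 is described as suggested guidance for drug-related toxicity, to be applied with clinical judgment. As a general matter, once toxicity is back to grade 1 or less, "the investigator may resume full dosing if clinically indicated".
- **Section 7.5.1.** The instruction is: "Interrupt or stop ponatinib immediately for vascular occlusion". For arterial events: "If a participant experiences an arterial thrombotic event while receiving ponatinib, the subject should discontinue ponatinib permanently". For venous events: "In participants with venous thrombosis or occlusion, a benefit-risk consideration should guide a decision to restart ponatinib therapy", with the Principal Investigator involved. None of these sentences is limited by grade.

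Section 7.4 is also relevant. One condition for dose escalation is that "the participant has not experienced any vascular toxicities of any grade".

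**The concern.** Vascular occlusion is listed in Section 2.1 among the adverse events of special concern. That section reports fatal and life-threatening occlusion within two weeks of starting treatment, and at doses as low as 15 mg per day. For such a toxicity the action at first recognition should be readable in one way only.

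A site that works from the table finds no vascular row, goes to the General row, and for a grade 1 or transient grade 2 event takes no action. A site that works from Section 7.5.1 interrupts or stops. Both can say that they followed the protocol. The first consequence is for the participant's safety. The second is for the data: with three centres named in Section 13.2 and 20 participants in all, interruptions and discontinuations for vascular toxicity could partly reflect which page a site consulted, and a departure from either passage could not be classed cleanly as a protocol violation.

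**Working it through.** The protocol states no figure on this point to reproduce, and the question is one of text. The passages set side by side:

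| Drug-related event | Table 7.1, General row | Section 7.5.1 | Result |
|---|---|---|---|
| Arterial, grade 1 or transient grade 2 | No intervention | Interrupt or stop at once; permanent discontinuation | Contradiction |
| Venous, grade 1 or transient grade 2 | No intervention | Interrupt or stop at once; restart by benefit-risk decision | Contradiction |
| Either, persistent grade 2 or grade 3-4 | No line visible | As above | No contradiction |

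Step 1: does the General row reach vascular events? Its scope is every nonhematologic toxicity without its own row further down. No vascular or thrombotic row follows, so on the wording it does.

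Step 2: does separate treatment in Section 7.5 take a toxicity out of the General row? Not by itself. Hypertension (7.5.9) and QTcB prolongation (7.5.10) have their own subsections, and both send the reader back to the general nonhematologic guidance in Table 7.1. A toxicity can therefore be discussed in Section 7.5 and still be managed under that row.

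Step 3: does anything say that Section 7.5.1 overrides the table? No. Section 7 names both sources. Section 7.5.1 does not mention Table 7.1, and Table 7.1 does not mention Section 7.5.1.

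Step 4: does the protocol contemplate low-grade vascular events? The escalation criterion in Section 7.4 refers to vascular toxicity at any grade, so grading down to the lowest level is foreseen. It does not show that such events are expected, and vascular toxicity may be a wider term than occlusion.

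Step 5: does the resume sentence in Section 7.3 conflict with the arterial rule? It is a permission with three qualifiers: it applies in general, the investigator may act on it, and only if clinically indicated. Section 7.5.1 is a specific rule for one toxicity, and a specific prohibition can stand as an exception to a general permission. What is missing is a sentence in Section 7.3 that says so. For venous events the two are compatible, although Section 7.5.1 adds the Principal Investigator's involvement.

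**The case against.** The strongest case against is that a careful reader would follow Section 7.5.1. It is specific, names the toxicity and calls for immediate action, whereas Table 7.1 is only suggested guidance. Where Section 7.5 wants the table used, it says so (7.5.2, 7.5.7, 7.5.9 and 7.5.10). Section 7.5.1 contains no such pointer and so reads as a stand-alone rule. This is a fair account of what the authors may have intended, and it lowers the chance that sites would diverge. It does not remove the conflict, because the rule that the specific text prevails is the reader's inference and is stated nowhere.

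The objection also guards against two stronger readings.

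A reader might infer that Section 7.3 directly contradicts permanent discontinuation after an arterial event. The text does not support this. The resume sentence is a hedged default, and Section 7.5.1 can stand as an exception to it.

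A reader might also infer that sites could take no action on a life-threatening occlusion. The table does not say that either. Its no-intervention entry is limited to grade 1 and transient grade 2. For higher or persistent grades the General row shows no line in the copy reviewed. Lines may have been lost in conversion from PDF, since 7.5.9 and 7.5.10 rely on interruption and reduction guidance there. Any such lines would not alter the low-grade conflict.

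**Conclusion.** The point holds, limited to drug-related grade 1 or transient grade 2 vascular occlusion. For those events Table 7.1 and Section 7.5.1 prescribe opposite actions with no stated precedence. Section 7.3 has a missing cross-reference, which is a lesser matter.

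The number of participants affected cannot be derived from the documents. A reader might infer a count from the phase 2 rates in Section 2.1: any occlusion 20 × 109/449 = 4.9, arterial 20 × 91/449 = 4.1, venous 20 × 23/449 = 1.0. Those figures do not measure this problem, for two reasons.

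- They come from CML/ALL patients in a trial at 45 mg daily. This trial starts at 30 mg, excludes prior arterial thrombotic disease (3.2.11) and venous thromboembolism within 6 months (3.2.14), and calls for thromboprophylaxis and a statin (6.11). Carrying the rates over would be an assumption.
- No grade split of vascular events is given. Even if the rates carried over, a low-grade share anywhere between 0 and 1 would put the expected number between 0 and 4.9, which is uninformative.

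The case for correction rests on the seriousness of the toxicity and the small effort needed, and does not depend on a projected count. The conclusion assumes that Table 7.1 has no vascular row beyond the text available for review.

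**What to change.** The sponsor should reconcile Table 7.1, Section 7.3 and Section 7.5.1 and state which passage governs vascular events, at which grades. Three edits would then follow:

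- a vascular occlusion line in Table 7.1 that points to the single rule the sponsor confirms;
- a cross-reference to that rule beside the resume sentence in Section 7.3;
- if useful, a sentence in the opening of Section 7 on precedence between the table and Section 7.5.

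Which clinical rule should apply is for the sponsor to decide, and none is proposed here. The cost is one table line and one or two cross-references in an amendment, with the IRB approval that Section 12.1 requires. Sample size, endpoints and the response analysis are unaffected.

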### **7.5.2 Myelosuppression**

Neutropenia, anemia, and thrombocytopenia have all been commonly reported either together or individually in patients treated with ponatinib. While myelosuppression can occur any time during treatment, its onset most commonly occurs within the first month on treatment. These events can typically be managed with supportive care and, if felt to be treatment related, either a reduction or interruption of treatment with ponatinib should occur (see Table 7.1). Rarely, one or more cytopenias can lead to permanent discontinuation of treatment. The use of hematopoietic growth factors such as granulocyte colony-stimulating factor (G-CSF) or granulocyte-macrophage colony-stimulating factor (GM-CSF) is permitted on study; these agents may be used to support blood counts as clinically indicated to minimize treatment interruptions or repeated dose reductions.

The important clinical adverse event of febrile neutropenia falls under the broad category of myelosuppression. If a patient's individual risk factors place them at high risk of developing febrile neutropenia, primary prophylaxis use of colony-stimulating growth factors for the prevention or reduction of febrile neutropenia is recommended according to the published NCCN guidelines [NCCN Guidelines Version 1.2012 – Myeloid Growth Factors].

### **7.5.3 Rash and/or Pruritus**

Skin rashes have been commonly reported to be associated with ponatinib. The vast majority of the skin events are self-limiting or manageable with antihistamines or topical steroids, and do not result in discontinuation. In more severe cases, a short course of oral corticosteroids may be used until the rash has improved or resolved.

In patients treated with ponatinib, the most common skin manifestations are an acneiform dermatitis or diffuse maculo-papular rash that is non-pruritic. Occasionally, patients treated with ponatinib have been reported to have a dry, flaky or exfoliative type of rash or a psoriasiform dermatitis. Rarely, an erythema multiforme type of rash has been associated with ponatinib.

### **7.5.4 Pancreatitis and Amylase or Lipase Elevations**

Pancreatitis (symptomatic abdominal pain associated with pancreatic enzyme elevation) and/or elevations in lipase and amylase are known AEs associated with ponatinib. Pancreatitis was reported in 7% of patients in the phase 2 study of ponatinib and 12% in the phase 1 dose-escalation study. Most cases of pancreatitis or elevated pancreatic enzymes occur within the first month of treatment with ponatinib. The events are generally uncomplicated and reversible and can be managed with a brief interruption of treatment and standard medical therapies. Almost all patients are able to continue on with ponatinib treatment at the same or a reduced dose once the event has improved to grade 1 or resolved.

Patients with low-grade (1 or 2) elevation in amylase can be continued without dose reduction but should be monitored closely with serial enzyme level determinations.

### **7.5.5 Diarrhea, Nausea, and Vomiting**

Diarrhea is a less-common side effect of ponatinib. The use of anti-diarrhea medications is permitted. Participants who experience  $\geq$  grade 2 diarrhea may begin loperamide at its standard treatment schedule (4 mg orally x 1, then 2 mg orally after each loose stool, up to a maximum of 16 mg/day).

Nausea and vomiting are not commonly seen with ponatinib. The use of an antiemetic prophylactically is not recommended. However, if a participant is symptomatic, appropriate antiemetic medications may be used as clinically indicated.

### **7.5.6 Constitutional Symptoms / Joint Pain**

Certain constitutional symptoms such as myalgia, arthralgia, headache, weakness, fatigue, asthenia, and low grade fever have been commonly reported with ponatinib. For patients treated with ponatinib, these symptoms have been reported mainly at the initiation of treatment. They are typically short lived (<2 weeks), and are seldom, if ever, reported beyond the first month of treatment. These AEs are most commonly low grade (grade 1 and 2) and are self-resolving without the need for dose interruption or dose reduction when they do occur. Most patients can be maintained on the current dose of ponatinib, uninterrupted, and their symptoms can be managed with a short course of oral analgesics, corticosteroids, and/or anti-pyretics as clinically indicated. If dose interruption is indicated, patients can resume the same dose of ponatinib typically without recurrence of symptoms once the original episode has improved or resolved.

### **7.5.7 Hepatotoxicity**

Hepatotoxicity, most commonly manifested by reversible transaminase and alkaline phosphatase elevation and hyperbilirubinemia, has been observed with ponatinib. Monitoring of hepatic function is recommended and management of laboratory abnormalities should be managed with dose interruption and/or dose reduction according to [Table 7.1](#).

### **7.5.8 Severe Congestive Heart Failure and Left Ventricular Dysfunction**

Severe congestive heart failure (CHF) and left ventricular (LV) dysfunction have been reported in patients taking ponatinib. Patients with cardiac disease or risk factors for cardiac disease should be monitored carefully and any patient with signs or symptoms consistent with cardiac failure should be evaluated and treated.

### **7.5.9 Hypertension**

Blood pressure should be monitored at each visit. Hypertension (HTN) by at least two blood pressure measurements should be graded according to CTCAE version 4.0. For participants who develop HTN or worsening HTN during study treatment, anti-hypertensive medication should be initiated or optimized to achieve target blood pressure before interruption or dose reduction of the study treatment at the discretion of the investigator. If hypertension is persistent despite adequate anti-hypertensive therapy including titration of anti-hypertensive medication or introduction of additional anti-hypertensive medications, or if grade 4 HTN develops, dose interruption and reduction is recommended according to Dose Modification Guidelines for general non-hematologic AEs in [Table 7.1](#).

### **7.5.10 Prolonged QTcB**

If a prolongation of QTcB is observed, it is important to perform serum electrolyte analysis (including potassium, calcium, and magnesium) and correct any significant abnormalities with supplements if below normal limits. It is also necessary to review all concomitant medications the participant is on and discontinue medications that are known or suspected to cause QT prolongation.

If no contributing reason is identified and the reason for QTcB prolongation is believed to be due to study medication, dose interruption and reduction guidelines for general non-hematologic toxicities in [Table 7.1](#) for ponatinib should be followed. Additionally, weekly ECG monitoring is recommended for 4 weeks upon resumption of study drug, then monthly for 6 months, and then per the routine ECG schedule.

## **8 Study Calendar**

[Table 8-1](#) lists all of the assessments and indicates with an “X” the visit when they are performed. All data obtained from these assessments must be supported in the participant’s source documentation and recorded on the corresponding eCRF pages.

**Table 8-1 Schedule of Events**

Assessment 	Baseline 	Cycle 1		Cycle 2 Day 1	Every 4 weeks (Cycle 3-10)	Every 8 weeks (Cycle 3-10)	Every 6 weeks (Cycle 11+) 	End of Treatment	30 Days After End of Treatment	Follow- up
		Day 1	Day 15							
Informed consent	X									
Demographics	X									
Inclusion / Exclusion Criteria	X									
Medical & Surgical History	X									
Diagnosis & Extent of Tumor	X									
Prior Cancer Therapy	X									
Tumor Mutational Status 	X									
Smoking Status	X									
Vital Signs	X	X	X	X	X		X	X	X	
ECOG Performance Status	X	X	X	X	X		X	X	X	
Physical Exam	X	X		X	X		X	X	X	
Electrocardiogram (ECG) 	X				(X) 		(X) 	X		
Cardiac Imaging (ECHO)	X				(X) 					
Hematology	X	X	X	X	X		X	X	X	
Serum Chemistry	X 	X	X	X 	X		X	X	X	
Pregnancy Test	X							X		
PK Sample		X 		X 						
Concomitant Medications	X	X	X	X	X	X	X	X	X	
Disease Assessment 	X					X	X 	X		X 
Survival										X

Footnotes for Schedule of Events:

- 1 This schedule of events table is meant to provide a convenient display of the timing and scope of required assessments expected at each visit. It is not a comprehensive description of each assessment. A complete list of all study related assessments as well as a detailed description of which is expected can be found in Section 5.
- 2 Tumor mutational status: Any previously identified RET translocation, method of identification, and the dates of identification must be recorded. If available, the presence of additional mutations such as KRAS, EGFR, ALK or ROS should be recorded.
- 3 All ECGs should be 12-lead ECGs. ECGs are to be performed at screening, Cycle 4 Day 1, Cycle 7 Day 1, and Cycle 13 Day 1. Please see [Table 7.1](#) and [Section 7.5](#) for a description of ECG monitoring requirements if a prolonged QTcB develops in the course of the study period.
- 4 An additional echocardiogram may be performed on Cycle 4 Day 1 at the discretion of the Investigator based upon participant symptoms.
- 5 Triglycerides will be collected during the baseline assessment only.
- 6 Chemistries, including serum lipase, should also be drawn on Cycle 2 Day 15.
- 7 PK samples will be collected pre-dose on Cycle 1 Day 1 and Cycle 2 Day 1. Additional PK samples will be collected on Cycle 1 Day 1 only at the following time-points: 1, 2, and 4 hours ( $\pm$ 10 minutes), and 6 and 8 hrs ( $\pm$ 20 minutes) post dose. Whole blood will be collected in EDTA-K2 tubes (lavender top). Refer to site-specific laboratory manual for further details.
- 8 Disease assessments will initially be performed at 8 week intervals (after cycle 2 [at the beginning of cycle 3 in the table above], after cycle 4 [at the beginning of cycle 5], and so on until cycle 11). From cycle 11 forward, disease assessments will be performed at 12 week intervals (after cycle 13 [at the beginning of cycle 14] and so on). Disease assessments may be limited to the sites of disease. RECIST-defined responses will be confirmed with a repeat assessment in  $\geq$ 4 weeks (See [Section 9](#)). Disease assessments will also be performed at the End of Treatment.
- 9 Any participant who discontinued study treatment for any reason other than disease progression, death or withdrawal of consent will continue to have disease assessments every 12 weeks ( $\pm$ 14 days) until the participant starts another anti-cancer therapy.
- 10 From cycle 11 forward, study visits will be every 6 weeks but disease assessments will be every 12 weeks (after cycle 13, 16, etc).
- 11 Baseline procedures are to be obtained within 14 days of the start of study treatment with the exception of obtaining informed consent and baseline disease assessments, which should be obtained within 28 days prior to the start of study treatment.
- 12 All assessments and procedures (with the exception of baseline) have a  $+$ - 3 day window.

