16. **Concomitant Medications:** Concomitant medications for all ongoing medical history conditions or AEs must be reported from the date the informed consent is signed until at least 30 Days After the End of Treatment, and for all concomitant medications related to

serious or study drug-related toxicities until the medication is no longer taken or until patient contact discontinues.

17. **Pregnancy Test:** The pregnancy test must be a beta-human chorionic gonadotropin ( $\beta$ -HCG) test and either urine or serum can be used. Women who are not of childbearing potential (status post-hysterectomy, status post-bilateral oophorectomy, or post-menopausal [defined as amenorrhea for at least 12 months]) and men do not need to have the test performed. The test must be known to be negative prior to the study drug administration and be performed within 7 days prior to first study drug administration.
18. **Disease Assessment:** At screening, disease assessment must include imaging of the chest, abdomen, pelvis and brain using appropriate radiological procedures (computed tomography [CT] scan, MRI scan) and physical examination (for palpable lesions). Brain imaging is required at entry. Follow-up brain imaging need not be routinely performed in the absence of findings. Target and non-target lesions must be selected at study start and followed throughout the course of treatment for response assessment according to RECIST guidelines (See [Section 9](#)). Imaging assessment is also required to be performed at the End of Treatment. Note: RECIST-defined responses will be confirmed with an imaging assessment  $\geq 4$  weeks later.
19. **Survival:** All participants should be followed for survival every 3 months, up to 2 years after the initial dose of ponatinib.

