### **9.1.3 Response Criteria**

#### ***Evaluation of Target Lesions***

**Complete Response (CR):** Disappearance of all target lesions. Any pathological lymph node must have reduction in short axis to < 10 mm.

**Partial Response (PR):** At least a 30% decrease in the sum of the diameters of target lesions, taking as reference the baseline sum diameters.

**Progressive Disease (PD):** At least a 20% increase in the sum of the diameters of target lesions, taking as reference the smallest sum on study with at least a 5 mm absolute increase in the sum of all lesions. The appearance of one or more new lesions\* denotes disease progression.

Stable Disease (SD): Neither sufficient shrinkage to qualify for PR nor sufficient increase to qualify for PD, taking as reference the smallest sum diameters while on study.

Unknown (UN): Assessment of target lesions cannot be made due to insufficient or unevaluable data. In this case, a concise explanation must be given.

**Note:** If tumor response data is missing for target lesions, the overall assessment must be UN unless there is new disease that would result in an overall assessment of PD. However, if there is missing or unevaluable data for non-target lesions, but data is available for all target lesions, the overall response for that time point will be assigned based on the sum LD of all target lesions. Additionally, the assessment of CR cannot be made if there is missing or unevaluable data for non-target lesions. In this case, the overall assessment would be PR.

**\*Definition of New Lesion:** The finding of a new lesion should be unequivocal (i.e. not due to difference in scanning technique, imaging modality, or findings thought to represent something other than tumor (ex: new bone lesions may be healing or flare of pre-existing lesions)). However, a lesion identified on a follow-up scan in an anatomical location that was not scanned at baseline is considered new and will indicate PD. If a new lesion is equivocal (because of small size, etc.), follow-up evaluation will clarify if it truly represents new disease and if PD is confirmed, progression should be declared using the date of the initial scan on which the lesion was discovered.

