### **For Participants with Measurable Disease (i.e., Target Disease)**

Target Lesions	Non-Target Lesions	New Lesions	Overall Response	Best Overall Response for when Confirmation is Required:
CR	CR	No	CR	$\geq 4$ wks confirmation
CR	Non-CR/Non-PD	No	PR	$\geq 4$ wks confirmation
CR	Not evaluated	No	PR	$\geq 4$ wks confirmation
PR	Non-CR/Non-PD/Not evaluated	No	PR	
SD	Non-CR/Non-PD/Not evaluated	No	SD	Documented at least once $\geq 4$ wks from baseline
PD	Any	Yes or No	PD	No prior SD, PR or CR
Any	PD*	Yes or No	PD	
Any	Any	Yes	PD	

\* In exceptional circumstances, unequivocal progression in non-target lesions may be accepted as disease progression.

Note: Participants with a global deterioration of health status requiring discontinuation of treatment without objective evidence of disease progression at that time should be reported as "*symptomatic deterioration*". Every effort should be made to document the objective progression even after discontinuation of treatment.

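### Table 8-1 footnote 8 lets follow-up scans omit uninvolved regions although a new lesion anywhere counts as progression, so PFS, and less so DCR and ORR, can be biased upward

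*Combined protocol and SAP*

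**What the plan says.** **Screening.** Section 5.1 item 18 sets the baseline field: "At screening, disease assessment must include imaging of the chest, abdomen, pelvis and brain using appropriate radiological procedures".

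**Follow-up in Section 5.1.** Item 18 relaxes one region only: "Follow-up brain imaging need not be routinely performed in the absence of findings". It adds: "Target and non-target lesions must be selected at study start and followed throughout the course of treatment for response assessment". It does not list the body regions that a follow-up scan must cover.

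**Follow-up in Table 8-1.** Footnote 8 sets the 8-week and later 12-week schedule and then allows: "Disease assessments may be limited to the sites of disease". The same footnote covers the End of Treatment assessment and asks for no wider field there. Footnote 1 calls the table a convenient summary and sends the reader to Section 5 for the detail.

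**Scoring.** In Section 9.1.3 the following is progression, with no limit on where it occurs: "The appearance of one or more new lesions". In the best-overall-response table for participants with measurable disease, every CR, PR and SD row has No under New Lesions. The non-target column allows a not-evaluated entry; the new-lesion column does not. The section has missing-data rules for target and non-target lesions, but none for new lesions that could not be assessed.

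**Central review.** Section 9.1.6 has an imaging core read the scans for RECIST.

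**The concern.** The scoring rule presumes that new lesions have been ruled out across the body. The imaging rule allows that search to be confined to regions with known disease. A participant whose disease is confined to the chest could be followed by chest CT alone. A new liver or adrenal lesion would then be outside the image, the form offers nothing but No for new lesions, and the participant would stay PR or SD.

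The error has one direction. An unseen new lesion can delay or remove a progression but cannot create one. There is no control arm in which the error could cancel. Central review cannot repair it, because it reads only the images that were taken. The permission is discretionary, so coverage can differ between the three sites named in Section 13.2.

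**Working it through.** **1. The texts side by side**

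| Question | Section 5.1 item 18 | Table 8-1 footnote 8 | Section 9.1.3 |
|---|---|---|---|
| Which regions at follow-up? | Only the brain is exempted, if clear | Sites of disease suffice | Not stated |
| Where does a new lesion count? | – | – | Anywhere |
| What if a region was not imaged? | – | – | No entry for new lesions |

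If footnote 8 already exempted every uninvolved region, the brain exemption in item 18 would be redundant. No section requires scheduled follow-up imaging of uninvolved regions.

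**2. Which endpoints are exposed**

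- PFS: any progression that first appears outside the scanned field, at any time on study.
- DCR: only an early progression that rests solely on such a lesion. One participant is 1/20 = 5 percentage points.
- ORR: only if the target lesions meet PR or CR while the unseen lesion is already present at response or at confirmation 4 or more weeks later. Best response counts only up to progression, so a lesion arising after a confirmed response leaves ORR unchanged.
- One-year OS rate: not affected.

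**3. The plan's own figures**

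Inputs from Section 13.1: n = 20, success at 4 or more responses, ORR 10% (null) and 30% (alternative). Exact binomial:

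- P(X ≥ 4 | 20, 0.10) = 1 − (0.1216 + 0.2702 + 0.2852 + 0.1901) = 0.133. The plan says 13%.
- P(X ≥ 4 | 20, 0.30) = 0.893. The plan says 89%.

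Both reproduce.

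**4. ORR sensitivity**

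Let m be the share of apparent responders who would be PD if the missed lesion had been seen. This share is assumed; the documents give no figure. Observed rate = true rate / (1 − m), for example 0.10 / 0.90 = 0.111.

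| m | Observed ORR, true 10% | P(≥ 4/20) | Observed ORR, true 30% | P(≥ 4/20) |
|---|---|---|---|---|
| 0 | 10.0% | 13.3% | 30.0% | 89.3% |
| 5% | 10.5% | 15.2% | 31.6% | 91.8% |
| 10% | 11.1% | 17.5% | 33.3% | 94.0% |
| 20% | 12.5% | 23.5% | 37.5% | 97.3% |

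**5. DCR sensitivity**

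Assume a true DCR of 60% and that a share s of the remaining 40% is missed. Observed DCR = 0.60 + 0.40 × s, which is 62%, 64% and 68% for s = 5%, 10% and 20%.

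**6. PFS sensitivity**

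Assume exponential PFS with a true median of 6 months (λ = ln 2 / 6 = 0.1155). Let a share s of events be detected D months late. For D below the median, the observed median is 6 + ln(1 − s + s·e^(λD)) / λ. Two 28-day cycles are 56 / 30.44 = 1.84 months; four are 3.68 months.

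| s | 2 cycles late | 4 cycles late |
|---|---|---|
| 10% | 6.20 months | 6.45 months |
| 20% | 6.40 months | 6.87 months |

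For example, with s = 10% and D = 1.84: ln(0.90 + 0.10 × 1.237) / 0.1155 = 0.20.

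**The case against.** The strongest reply has four parts.

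- **Footnote 8 is a permission.** A reader might infer that new lesions elsewhere are never looked for and that the endpoints are biased. The documents support only that they may go unimaged where a site uses the permission. New lesions inside the scanned field are still seen, and physical examination at most visits and symptom-led imaging remain. The footnote also does not say that the sites meant are those at baseline, though that is the natural reading. This part stands.
- **Section 5.1 may govern.** Footnote 1 defers to Section 5, and item 18 exempts only the brain. That makes the defect partly a conflict between two places. But item 18 never states the other follow-up regions, so deferring to it does not close the gap.
- **The size can be overstated.** A reader might take one participant wrongly kept as PR as the likely effect: P(X ≥ 3 | 19, 0.10) = 0.295 against 13.3%. That assumes one false responder with certainty, which nothing in the documents supports. Nor do they support saying that each missed progression is dated at least one scan late, because symptom-led imaging or death (a PFS event in Section 1.5) can come first.
- **The exposed endpoints are exploratory.** Section 13.3 says so for the secondary endpoints, and the primary endpoint is reached only by the narrow route above. This limits the weight of the point. But PFS and DCR are stated objectives, and images that were not taken cannot be recovered later.

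Two other rules in Section 9.1.3 should not be used as support. The one ending "is considered new and will indicate PD" concerns locations not scanned at baseline, whereas here the region was scanned at baseline and dropped later. The one beginning "In exceptional circumstances, unequivocal progression in non-target lesions may be accepted as disease progression" concerns existing lesions, not new ones.

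**Conclusion.** The point holds as a one-directional gap that the plan permits. It is not a demonstrated bias. Where footnote 8 is used, PFS can be too long and DCR too high. ORR can be too high only if the unseen lesion is present by response or its confirmation, so a reader should not infer that ORR is as exposed as PFS. The End of Treatment scan is not a reliable backstop, because the same permission covers it.

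The size is unknown. On assumed shares of 5, 10 and 20% of apparent responders with a missed lesion, the false-positive chance at a true ORR of 10% goes from 13.3% to 15.2, 17.5 and 23.5%. On an assumed 6-month median with 10 to 20% of events found 2 to 4 cycles late, observed median PFS is about 6.2 to 6.9 months. These figures show how the results respond to the assumptions; they do not estimate this trial's bias. The change is worth making because it is cheap and the loss cannot be repaired afterwards.

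**What to change.** Replace the footnote 8 sentence with a minimum field, for example: every scheduled disease assessment, and the End of Treatment assessment, images at least the chest and abdomen by the same method as at baseline, plus any other region that was involved at baseline or is clinically suspected. Keep the item 18 exemption for routine brain imaging. State the same field in Section 5.1 item 18, and say in Section 9.1.3 how a time point is scored when a required region was not imaged, so that the three places agree.

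This narrows the gap without closing it: an uninvolved pelvis and a clear brain would still not be imaged routinely, and the plan should state that as an accepted limit. For assessments already done with a narrower field, report the coverage and present PFS, DCR and ORR with that limitation.

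The cost is a short amendment, plus slightly more radiation and expense in the same CT session for participants with disease confined to the chest. No new visit or reader is needed.
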